**ATT. SAFETY DEPARTMENT**  
e-mail: **CCI** [REDACTED]

The investigator will collect information about the SAE on the respective form. At least these **four elements are mandatory** always to report any adverse event must include the following:

- Name or any identifier of a **reporter**
- **Subject** ID number
- At least one **suspect drug**: current dose, route, dates
- **Adverse Event** information:
  - **Adverse Event Term Seriousness Criteria**
  - **Causality assessment**

### 11.3.3. Reporting of serious adverse events (SAEs) to Health Authorities

The sponsor is responsible for notifying to the Regulatory Health Authorities according to applicable regulations of all suspected unexpected serious adverse reactions and which occurred in the clinical trial. This communication shall be made within the time limits established by legislation.

### 11.3.4. Follow-up of AEs and SAEs

After the initial notification of an AE or SAE, the investigator is required to follow up each case and obtain more data on the patient's state. All the AEs and SAEs documented in previous visits must be reviewed in subsequent visits. All AEs and SAEs must be monitored until their resolution. This is applicable to all the patients, including those who withdraw early.

### 11.3.5. AEs or SAEs that occur after the study ends

Post-study AEs or SAEs are defined as any event that occurs outside the Follow-up period of detection defined in the protocol. The investigator is not required to actively seek out AEs or SAEs in patients who have participated in the clinical trial in the past. Nevertheless, if the investigator comes to know of the existence of any AE or SAE, including the death of the patient at any time after a patient has left the study, and this AE or SAE is considered related to the study drug, the investigator must notify the sponsor promptly.

### **11.3.6. Events of special interest**

Binimatinib is an investigational drug and current knowledge of the AEs associated with this compound is limited. As with any new chemical entity, there is always potential for unexpected AEs, including hypersensitivity reactions.

The most frequently reported AESI for binimatinib groupings ( $\geq 20.0\%$  of patients in either population) were retinopathy excluding RVO, muscle enzyme/protein changes, liver function test abnormalities and rash. Grade 3/4 AESIs reported for  $\geq 5.0\%$  of patients in either population were in the groupings of liver function test abnormalities, muscle enzyme/protein changes and hypertension.

#### **Ocular AESIs**

Retinopathy excluding RVO events were the most common AESI grouping reported. Retinopathy excluding RVO events reported in  $> 5.0\%$  of patients were vision blurred, retinopathy, subretinal fluid, retinal detachment, visual field defect and macular edema. Events in the RVO grouping were uncommon.

#### **Muscle Enzyme/Protein Changes and Myopathy/Rhabdomyolysis-Related AESIs**

Muscle enzyme/protein changes were frequently observed, although Grade 3/4 events were less common in patients. All patients with an event in the muscle enzyme/protein changes grouping had at least 1 event reported under the PT of blood CK increased. No other muscle enzyme/protein changes by PT were reported in  $> 5.0\%$  of patients in either population.

Events in the myopathy grouping were reported; few patients had a Grade 3/4 event. The myopathy event reported in  $> 5.0\%$  of patients in either population by PT was myalgia.

Events in the rhabdomyolysis grouping were uncommon.

Symptomatic muscle-related AEs reported in the myopathy and rhabdomyolysis groupings that occurred within 15 days before to 30 days after the worst laboratory CK elevation were analyzed. Around 6% of patients with a worst post-baseline laboratory CK value  $\geq$  Grade 1 had at least one symptomatic muscle-related AE reported.

#### **Liver-related AESIs**

Events in the liver function test abnormalities grouping were reported (between 20-26%) and about half of the patients with an event in the liver function test abnormalities grouping experienced at least 1 Grade 3/4 event. The events in the liver function test abnormalities grouping reported in  $> 5.0\%$  of patients were GGT increased, ALT increased and AST increased.

Events in the hepatic failure grouping were uncommon.

#### **Dermatologic-related AESIs**

Rash events are frequently reported with single-agent binimatinib treatment.

Events in the skin infections grouping were reported; few patients had a Grade 3/4 event. The skin infection events reported in >2.0% of patients in either population by PT were folliculitis and cellulitis.

Nail disorder events were infrequently reported; no patients had a Grade 3/4 event in this grouping.

Severe cutaneous adverse reactions were rarely observed. No severe cutaneous reaction events were Grade 3/4 in severity. These events were reported under the PTs of dermatitis exfoliative, erythema multiforme, toxic skin eruption, dermatitis bullous and erythema multiforme.

### **Hemorrhage AESIs**

Hemorrhage events were reported; Grade 3/4 events were less common. The hemorrhage events reported in >2.0% of patients in either population were hematuria, rectal hemorrhage and hematochezia.

### **Peripheral Edema AESIs**

Peripheral edema events were reported in 11-16% of patients; few patients had a Grade 3/4 event. The peripheral edema event reported in >2.0% of patients was edema peripheral.

### **Hypertension AESIs**

Hypertension events were reported in 9-12% of patients and about half of the patients with an event in the hypertension grouping experienced at least 1 Grade 3/4 event. The PT of hypertension was the most frequently reported event (> 2.0% of patients) in the grouping.

### **Cardiac-related AESIs**

Left ventricular dysfunction events were reported in 6-8% of patients, with few patients experiencing a Grade 3/4 event. The most frequently reported event was ejection fraction decreased.

Bradycardia events were infrequently reported (around 1%); none were reported as Grade 3/4. The most frequently reported event was sinus bradycardia.

### **Venous thromboembolism AESIs**

Venous thromboembolism events were reported in 2-4% of patients, with few patients (around 1%) experiencing a Grade 3/4 event. The most frequently reported event was pulmonary embolism.

### **Pneumonitis AESIs**

Events in the pneumonitis grouping were uncommon and were reported in 2 patients (interstitial lung disease and pneumonitis).

### **11.3.7. Pregnancy**

The investigator must report all pregnancies during the study, including follow up outcomes, within 24 hours of awareness.

Each pregnancy must be reported on a Pregnancy Report Form within 24 hours of becoming aware of the pregnancy. Pregnancy is not an AE, and therefore does not need to be reported as an AE unless there is a suspicion that the study drug may have interfered with the effectiveness of a contraceptive medication.

Any SAE that occurs during pregnancy must be recorded on the Pregnancy Report Form, reported as an SAE on the SAE Report Form (e.g., maternal serious complications, therapeutic abortion, ectopic pregnancy, stillbirth, neonatal death, congenital anomaly, birth defect) and reported to the Sponsor within 24 hours. Hospitalization for normal delivery of a healthy newborn should not be considered an SAE.

Any exposure during breast feeding must also be reported.

### **11.3.8. Special Situations: Abuse, Misuse, Medication Errors, Overdose, and Accidental or Occupational Exposure**

- Abuse: is the persistent or sporadic, intentional excessive use of the study treatment which is accompanied by harmful physical or psychological effects.
- Misuse: medicinal product is intentionally and inappropriately used not in accordance with the authorized/approved product information.
- Medication error: is any preventable incident that may cause or lead to inappropriate study treatment use or patient harm while the study treatment is in the control of the health care professionals or patients. Such incident may be due to health care professional practice, product labeling, packaging and preparation, procedures for administration, and systems, including the following: prescribing, order communication, nomenclature, compounding, dispensing, distribution, administration, education, monitoring, and use.
- Overdose: is a deliberate or accidental administration of study treatment to a study patient, at a dose greater than that which was assigned to that patient per the study protocol and under the direction of the Investigator. Study investigator should be notified of overdose immediately, and the patient should be observed closely for AEs. Associated AEs should be treated and monitored by the Investigator.
- Accidental /Occupational exposure: is the unintentional exposure to a study treatment as a result of one's professional or non-professional occupation, or accidental exposure to a non-professional to whom exposure was not intended (i.e., study product given to wrong patient).

Reporting Special Situations: All occurrences of abuse, misuse, medication error, overdose, and accidental or occupational exposure of study treatment must be reported on a Serious Adverse Event Report Form to the Sponsor within 24 hours of awareness regardless of whether or not an AE or SAE has occurred. If the abuse, misuse, medication error, overdose, or accidental / occupational exposure is associated with an AE, an SAE Report Form must also be submitted to the Sponsor within 24 hours of awareness.

## 12. STATISTICAL CONSIDERATIONS

### 12.1. General considerations

A comprehensive statistical analysis plan (SAP) will be prepared before database closure.

Continuous variables will be described by the mean, median, standard deviation, minimum and maximum. Categorical variables will be shown as absolute and relative distribution of frequencies and percentage. Also a 95% CI will be presented if this information is considered relevant to describe a singular variable.

### 12.2. Sample size

Patients with advanced TNBC that have received and experienced disease progression to the first/second line treatment are candidates to this trial. Patients that have received three or more treatment lines would be excluded.

Sample size has been calculated based on the primary objective of this clinical trial, to determine 3-months PFS of the palbociclib plus binimetinib in advanced TNBC, in patients with activation of ERK and/or CDK4/6.

Previous studies shown that the 3-months PFS in patients receiving chemotherapy in advanced TNBC was about 25% [44]. To accept the treatment efficacy we will assume that the 3-months PFS in patients treated with palbociclib plus binimetinib will be at least 50%. An overall sample size of 25 patients achieves 80% power at a 0.05 significance level (alpha) to accept the efficacy of palbociclib plus binimetinib in advanced TNBC. An accrual time of 12 months and follow-up time of 12 months (treatment and follow-up time) and 2 sided test have been considered in the sample size calculation.

Sample size has been calculated with one-sample survival method [45].

### 12.3. Analytical Populations

Safety population consists of all patients included in this study who received at least one dose of study treatment.

The efficacy population will be the basis for the primary endpoint analysis in this study; it consists of all patients included in this study that received at least one dose of study treatment and have at least one evaluation visit after received the first dose of treatment. This will also be the patient population used for the analysis of the secondary endpoints.

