## **8.2. Handling of Withdrawals**

The investigator will be requested to collect all patient data until she leave the study treatment. If a subject will be withdrawn by the Investigator or withdraws from the study, the Investigator will complete and report the observations as thoroughly as possible up to the date of withdrawal including the date of last treatment and the reason for withdrawal.

If the subject is withdrawn due to an adverse event, the Investigator will follow the subject until the adverse event has resolved or stabilized.

All patients who are withdrawn from the study should complete protocol specified withdrawal procedures.

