## **10.2. Study treatment visits**

Study patients will be evaluated weekly during the first 2 months and every 2 weeks thereafter.

The following procedures will be performed during study treatment:

- Tumor evaluation: PET-CT, CT and/or MRI (every 8 weeks)
- Physical examination: will be performed at screening and thereafter targeting symptoms in subsequent study visits
- Ophthalmological examination: Ask patient for changes in vision at every visit. If change in vision is reported, an ophthalmological examination must be performed preferably within 3 days. Ophthalmologic examination will be performed weekly during first cycle, biweekly during second cycle and every 4 weeks thereafter. Particularly for patients who experience any decrease in visual acuity, or symptomatic or asymptomatic retinal disorders including retinal detachment / RPED / serous retinopathy / retinal vein occlusion (Grade 1 analog to CTCAE v.5) have to undergo ophthalmologic examinations on day 1 of every cycle.
- Weight: in all study visits

- Vital Signs: pulse, blood pressure and temperature; every week during first two cycles, and days 1 and 15 of each cycle thereafter
- ECOG performance status (day 1 of every cycle)
- 12-lead ECG: if clinically indicated
- ECHO/MUGA: before start binimetinib treatment, 4 weeks after the start of treatment and every 12 weeks thereafter.
- Hematology: every week during first two cycles, and days 1 and 15 of each cycle thereafter
- Biochemistry: every week during first two cycles, and days 1 and 15 of each cycle thereafter. Safety laboratory tests can be collected up to 2 days prior to drug administration.
- TSH, fT3 y fT4: day 1 of every cycle. Free T3 and free T4 will only be measured if TSH is abnormal.
- Coagulation: day 1 of every cycle
- Urinalysis: day 1 of every cycle
- Serologies: if clinically indicated
- Pregnancy Testing: every 4 weeks (day 1 of each cycle). Pre-menopausal women of childbearing potential only
- Adverse events: in all study visits
- Concomitant medications: in all study visits
- Blood sample: two CPT tubes of 7 ml will be obtained before treatment administration at D1C1 and D1C2.

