### **10.3. End of treatment / early withdrawal**

The following procedures will be performed at end of treatment / early withdrawal visit:

- Tumor evaluation: PET-CT, CT and/or MRI, if patient stops study treatment for any reason other than disease progression
- Physical examination
- Ophthalmological examination
- Weight
- Vital Signs
- ECOG performance status
- 12-lead ECG: if clinically indicated
- ECHO/MUGA

- Hematology
- Biochemistry
- Serology
- TSH, fT3 y fT4
- Coagulation
- Urinalysis
- Pregnancy test
- Adverse events
- Concomitant medications
- Blood sample: two CPT tubes of 7 ml will be obtained at disease progression (a 2 weeks window is allowed from confirmation of disease progression).
- An image-guided biopsy will be done upon progression. The biopsy is allowed within 4 weeks after the confirmation of disease progression and in any case before starting the next line of treatment.

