### 12.4. Analysis of Primary Objective

Progression free survival (PFS) is defined as the time from the date of start treatment until objective tumor progression or death from any reason. Patients who have not progressed or died at the time of analysis will be censored at the time of the latest date of assessment from their last evaluable RECIST 1.1 assessment. PFS will be analysed according to the Kaplan-Meier method. Kaplan-Meier survival curves and median will be reported, along with associated 95% CI.

Three months PFS and the corresponding 95% CI will be provided.

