## 5. STUDY POPULATIONS

### 5.1. Definition of study populations to analyze

The following describes the different populations that will be used in the analyses process:

[figure not shown]
- **Efficacy population:** consists of all patients included in this study that received at least one dose of study treatment and have at least one evaluation visit after receiving the first dose of treatment. The efficacy population will be the basis for the primary endpoint analysis in this study. This will also be the patient population used for the analysis of the secondary endpoints.
- **Safety population:** consists of all patients who received at least one dose of the study treatment and had at least one valid post baseline safety assessment.

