### 8.2. Primary efficacy endpoint. PFS

Progression-free survival (PFS) is defined as the elapsed time, in months, between the start of treatment until the documentation of disease progression (radiological RECIST v1.1 or clinical) or death due to any cause, whichever occurs first. For subjects who are alive and not present disease progression at the time of data cut-off for analysis, PFS will be censored at the last tumor assessment date, if no one tumor assessment date is available PFS will be censored at start of treatment date.

PFS will be analyzed according to the Kaplan-Meier method. Kaplan-Meier survival curves and the median estimation will be reported, along with associated 95% CI. In order to response to primary end point, PFS rate at 3 month will be estimated and the 95% CI will be reported. In addition, PFS rate at 1 year with 95% CI will be calculated.

In addition, PFS will be evaluated by mutation ERK and CDK4/6.

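### The primary efficacy set drops treated patients who die before an undefined 'evaluation visit', although PFS counts those deaths; this biases 3-month PFS upward, probably by about 2 points or less

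*Protocol*

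**What the plan says.** Protocol 12.3 bases the primary endpoint, and the secondary endpoints, on patients who "received at least one dose of study treatment and have at least one evaluation visit after received the first dose of treatment". SAP 5.1 repeats the condition: patients must "have at least one evaluation visit after receiving the first dose of treatment". Neither document defines an evaluation visit.

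Protocol 12.4 measures PFS from the start of treatment "until objective tumor progression or death from any reason". SAP 8.2 counts "documentation of disease progression (radiological RECIST v1.1 or clinical) or death due to any cause". For patients who are alive and progression-free, SAP 8.2 adds that "if no one tumor assessment date is available PFS will be censored at start of treatment date".

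Protocol 10.2 says "Study patients will be evaluated weekly during the first 2 months and every 2 weeks thereafter", and the schedule in section 10 puts the first visit after day 1 at day 8, with a window of 2 days either way. Tumour evaluations are every 8 weeks. For early stoppers, Protocol 8.2 says "All patients who are withdrawn from the study should complete protocol specified withdrawal procedures". Protocol 10.3 asks for a scan at the end-of-treatment visit "if patient stops study treatment for any reason other than disease progression", and Protocol 10.4 schedules safety visits at day 30 and month 6 after the last dose.

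**The concern.** Membership of the primary set depends on something that happens after treatment starts: living long enough to be seen. The endpoint has no such condition. The two rules disagree about the same patient, the one who is dosed and dies before her first qualifying visit. Under the SAP definition, a patient with clinical progression and no qualifying visit would be lost in the same way.

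The trial has one arm and is set against an external 3-month PFS of about 25% (Protocol 12.2), so nothing offsets the exclusion. Because the term is undefined, who counts as evaluated could also be settled after outcomes are known in an open-label trial. What is at stake is an optimistic primary estimate at N = 25, where each patient carries 4 percentage points.

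**Working it through.** **Plan figures used.** From Protocol 12.2: reference 25%, target 50%, N = 25, two-sided 0.05, 80% power. A one-sample normal approximation gives N = (1.960·√(0.25·0.75) + 0.842·√(0.5·0.5))² / 0.25² = 25.8. That is within one patient of 25, so these figures serve as the base. The documents give no figure for early exclusions.

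**Which reading of the term.** Three things favour a clinic visit: Protocol 10.2 speaks of patients being evaluated weekly; scans have their own name, tumour evaluation; and the SAP 8.2 rule for patients with no tumour assessment implies that the set can contain patients without a scan. None of these rules out the week-8 tumour evaluation, so both readings are computed.

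**Direction.** With k treated patients dropped after dying before month 3, a true proportion S among 25 becomes S·25/(25 − k).

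| Dropped early deaths | True 25% | True 50% |
|---|---|---|
| 1 | +1.04 points | +2.08 points |
| 2 | +2.17 | +4.35 |
| 3 | +3.41 | +6.82 |

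An event-free patient with no assessment is censored at the start of treatment and contributes nothing whether kept or dropped. One narrow exception runs the other way: dropping a never-evaluated patient known to have died after month 3 lowers the estimate.

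**Expected size.** The documents give no survival figure for this population. Assume exponential survival with median m weeks. Entry requires a life expectancy above 24 weeks (Protocol 7.1), so m = 24 is taken as a pessimistic bound, with 48 and 72 as alternatives. The share dying by day t is q = 1 − 0.5^(t/(7m)), and the estimate after exclusion is S/(1 − q).

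*Clinic-visit reading, t = 10 (day-8 visit with its window):*

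| m (weeks) | q | Expected of 25 | P(≥1) | P(≥2) | 25% becomes | 50% becomes |
|---|---|---|---|---|---|---|
| 24 | 4.04% | 1.01 | 64% | 27% | 26.1% | 52.1% |
| 48 | 2.04% | 0.51 | 40% | 9% | 25.5% | 51.0% |
| 72 | 1.37% | 0.34 | 29% | 4.5% | 25.3% | 50.7% |

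*Week-8 reading, t = 56, deaths only. These are upper figures for deaths, because a patient scanned before she died would stay in:*

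| m (weeks) | q | Expected of 25 | 25% becomes | 50% becomes |
|---|---|---|---|---|
| 24 | 20.6% | 5.16 | 31.5% | 63.0% |
| 48 | 10.9% | 2.73 | 28.1% | 56.1% |
| 72 | 7.4% | 1.85 | 27.0% | 54.0% |

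On the week-8 reading, early clinical progression without a scan would add further losses.

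**Check under a different assumption.** Take a constant PFS hazard λ = −ln(S)/3 per month and let a fraction f = 5% to 20% of early PFS events be deaths before the qualifying visit (f is assumed). Then q = f·(1 − exp(−λt)). At day 8 this gives 0.07 to 0.57 patients and a shift of 0.1 to 0.6 points. At week 8 it gives 0.4 to 2.9 patients and 0.7 to 3.7 points.

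**Scale.** At 50% and N = 25 the 95% CI is about 2·1.96·√(0.25/25) = 39 points wide. Near the reference, one patient can still show: the exact 95% lower limit is 24.4% for 11/25 and 25.6% for 11/24. This is illustrative only, since neither document states a decision rule.

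**The case against.** The strongest reply is that the exclusion will usually be empty. Patients are seen weekly from day 8, must be ECOG 0–1 with adequate organ function, and are expected to live beyond 24 weeks. A constant hazard from day 1 therefore probably overstates deaths in the first 10 days. Even on these figures, the chance of no excluded death is 36%, 60% and 71% for medians of 24, 48 and 72 weeks. This stands. It is why the size is called small, and why 2 points is a likely size and not a limit.

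It is also fair that documented clinical progression usually implies that someone evaluated the patient, so that route adds little under the clinic-visit reading. Living early stoppers should mostly be retained by the withdrawal, end-of-treatment and day-30 visits. On the week-8 reading, the schedule table marks a tumour evaluation at end of treatment without the condition in Protocol 10.3, which would rescue some progressors. None of these helps a patient who has already died.

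An excluded death would not be hidden. SAP 4 puts all available data into listings and tabulations, and SAP 5.3 to 5.5 describe discrepancies in patient numbers, discontinuations and deaths, so a reader could recompute the estimate. The planned primary estimate would still omit her. The censoring rule in SAP 8.2 does not bring her back either, since it applies only to patients alive without progression.

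The replacement of early leavers under Protocol 8.3 covers the same period. It does not weaken the point: an all-treated set already includes dosed patients who are later replaced.

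**Conclusion.** The concern holds and is minor. The analysis set and the endpoint contradict each other on treated patients who die before a qualifying visit, in both documents, and no PFS analysis of all treated patients is planned. Apart from the narrow exception of a late death, the error favours the treatment.

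Under the clinic-visit reading the expected overstatement is 0.3 to 1.1 points at a true 25% and 0.7 to 2.1 points at a true 50%. A realised trial would more often show either no shift or about 1 to 2 points per excluded death. Under the week-8 reading, deaths alone could add up to 6.5 points at 25% and 13 points at 50%. The wording of the conflict is certain. The size rests on assumed survival, because the documents give no early-death rate. No change in the trial's conclusion is claimed.

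**What to change.** In Protocol 12.3 and SAP 5.1, define the primary efficacy set as all patients who received at least one dose, and say that dosed patients later replaced under Protocol 8.3 remain in it. Count deaths and documented progressions before the first evaluation as PFS events. Keep censoring at the start of treatment only for event-free patients without an assessment, as SAP 8.2 already provides. Retain the visit-based set as a sensitivity analysis and define the qualifying visit there.

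Two related points can be settled in the same edit. SAP 5.1 adds a valid post-baseline safety assessment to the protocol's one-dose safety population; align it with the protocol. SAP 7.1 reports exposure on the efficacy set; use the one-dose safety population instead.

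The cost is wording in Protocol 12.3 and SAP 5.1 and 7.1, and possibly a slightly less favourable estimate. No new data are required.
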